## 6.5.2. Other PK Parameters

The other PK Parameters are as follows and will be presented per age group by dose, and for individuals, where possible:

- Total area under the plasma concentration–time curve from 0 to infinity  $(AUC_{(0-\infty)})$ , if calculable
- Terminal plasma half-life  $(t_{\frac{1}{2}})$  if calculable
- Time of maximum observed plasma concentration  $(T_{max})$  per age group or patient, as data allows
- Clearance (CL/F) and volume of distribution ( $V_d/F$ ) per age group

Since Portola is no longer developing the Betrixaban program, no analyses will be performed for the other PK parameters.

## 6.6. Pharmacodynamic Analysis

## 6.6.1. Anti-fXa Activity

Anti-fXa activity during the first 24 hours post-dosing was not collected, and therefore will not be analyzed.

## 6.6.2. Thrombin Generation

Thrombin generation measurements were not collected, and therefore will not be analyzed.

#### 6.7. Safety Analysis

Safety will be assessed by examination of AEs, ECG, laboratory parameters, and vital signs.

## 6.7.1. Adverse Events

#### All AE analyses will be summarized by cohort.

AEs will be coded according to the Medical Dictionary for Regulatory Activities (MedDRA) dictionary. Treatment-emergent adverse events are defined as events that first occurred or

worsened after baseline following study treatment administration. In the analysis of Treatment-Emergent AEs (TEAEs), all events recorded as occurring before study treatment administration will be considered baseline conditions.

All TEAEs will be summarized by system organ class and preferred term.

The number of events, the number of patients, and the percentage of patients who experienced at least one TEAE will be presented.

TEAEs that lead to early withdrawals; and serious TEAEs will be summarized in the same manner.

Additionally, a listing table of all TEAEs will be provided.

### 6.8. ECG Parameters

A listing table will be provided for the ECG results.

### 6.9. Laboratory Parameters

A listing table, shift tables and number and percent of patients with values outside the normal range for the following labs will be provided by cohort:

- Hemoglobin
- Hematocrit
- Creatinine Clearance
- aPTT
- PT
- INR

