9.1.6.1. Hematology

Hematology assessments comprise a Complete Blood Count (CBC) and coagulation panel, as specified below:

- **CBC:** Absolute Neutrophil Count (ANC), basophils, differential, eosinophils, Hematocrit (HCT), Hemoglobin (Hgb), lymphocytes, Mean Corpuscular Hemoglobin (MCH), Mean Corpuscular Hemoglobin Concentration (MCHC), Mean Corpuscular Volume (MCV), monocytes, neutrophils, platelet count, Red Blood Cell (RBC) count, Red cell Distribution Width (RDW), reticulocyte, and White Blood Cell (WBC) count relative and absolute.
- **Coagulation Panel:** Activated Partial Thromboplastin Time (aPTT), Pro-Thrombin and International Normalized Ratio (PT/INR).

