9.1.6.2. Blood Chemistry

Blood chemistry analyses comprise a complete blood chemistry analysis and, if applicable, analysis of Gamma-Glutamyl Transpeptidase (GGT), as specified below:

• Complete Blood Chemistry Analysis: Alanine transaminase, albumin, Alkaline Phosphatase (ALK/ALP/ALKP), Aspartate Aminotransferase (AST), bilirubin (total), Blood Urea Nitrogen (BUN), calcium (Ca), chloride (Cl), creatinine, glucose, Lactate Dehydrogenase (LDH), potassium (K), SGOT (AST), SGPT (ALT), sodium (Na), uric acid, GGT.

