10.8. Safety

Safety and tolerability will be evaluated by clinical assessment of AEs and other safety measurements (vital signs, EKGs, laboratory tests, etc.). Treatment-emergent AE will be coded by the updated version of MedDRA and summarized as event rate by SOC and Preferred terms. Change in vital signs, laboratory tests, and EKG parameters from baseline to each post-dosing assessment will be derived for each patient. Appropriate summary statistics will be provided for each age group.

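### SAP 6.9 names no listing, shift table or out-of-range count for platelets or liver tests, although Protocol 10.8 promises each patient's change from baseline in laboratory tests

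*SAP*

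**What the plan says.** **Collection.** The Schedule of Assessments (Protocol Table 5) has local safety laboratory tests (hematology, coagulation, chemistry) at screening, Day -1, 24 h and 120 h. Protocol 7.4 and 7.5 repeat the two post-dose draws without restricting them to a cohort. The hematology panel in Protocol 9.1.6.1 includes "monocytes, neutrophils, platelet count, Red Blood Cell (RBC) count". The chemistry panel in Protocol 9.1.6.2 opens with "Alanine transaminase, albumin, Alkaline Phosphatase (ALK/ALP/ALKP), Aspartate Aminotransferase (AST), bilirubin (total") and ends with GGT, which its introductory sentence makes conditional on being applicable. Serum creatinine is in the same panel.

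**Protocol analysis.** Protocol 10.8 states: "Change in vital signs, laboratory tests, and EKG parameters from baseline to each post-dosing assessment will be derived for each patient". It adds summary statistics by age group and names no subset of tests. Protocol 10.3 leaves the full detail of planned analyses to the SAP.

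**SAP analysis.** SAP 6.9 covers a listing, shift tables and out-of-range counts in one sentence, which ends "values outside the normal range for the following labs will be provided by cohort". Six items follow: hemoglobin, hematocrit, creatinine clearance, aPTT, PT and INR. No other SAP section names an output for platelets or for any liver test. SAP 6.11, which records changes to conduct and planned analyses, covers the loss of Part 2 and of the pharmacodynamic measurements. It says nothing about laboratory reporting.

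**The concern.** Safety is an objective in both documents (Protocol 2.2, SAP 2.3), and Protocol 9.1 makes change from baseline in laboratory tests one of the ways it is judged. SAP 3.1 still counts serum chemistries among the Part 1 safety assessments. Followed as written, though, the SAP yields no patient-level platelet or liver result, and no table showing who moved from normal to abnormal after dosing.

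The reduction is also undeclared. The SAP states other cuts openly: the secondary PK parameters in 6.5.2, the pharmacodynamic assays in 6.6.1 and 6.6.2, and Part 2 in 6.11. ECG and vital signs each get a listing with no restriction to selected parameters (SAP 6.8 and 6.10). A reader comparing protocol with report could not tell whether platelets and liver tests were left out by decision or by oversight.

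With 3 patients in Cohort 1 and 18 in Cohort 2, patient-level output is the natural way to see an isolated rise in a transaminase or fall in platelets.

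**Working it through.** No figure in the plan needs reproducing. The check sets the two protocol panels against the SAP outputs.

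| Test | Drawn under | Listing, shift and out-of-range output in SAP 6.9 |
|---|---|---|
| Hemoglobin, hematocrit | Protocol 9.1.6.1 | Named |
| aPTT, PT, INR | Protocol 9.1.6.1 | Named |
| Serum creatinine | Protocol 9.1.6.2 | Indirect, through "Creatinine Clearance" |
| Platelets | Protocol 9.1.6.1 | Not named |
| ALT, AST, ALP, total bilirubin, GGT | Protocol 9.1.6.2 | Not named |

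**Step 1, tests affected.** Platelets: 0 of 1 named. Liver tests: 0 of 5 named. Together, 0 of 6.

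**Step 2, planned data affected.** Post-dose panels = patients × post-dose visits. Cohort 1: 3 × 2 = 6. Cohort 2: 18 × 2 = 36. Total: 6 + 36 = 42. With up to six tests per panel, 42 × 6 = 252 post-dose values at most on the planned numbers.

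**Step 3, does SAP 6.1 fill the gap?** SAP 6.1 says that all parameters are summarized descriptively, giving n, mean, median, SD, minimum, maximum and 95% CI for continuous variables. If that reaches tests not named in 6.9, it gives group summaries. Write x for a patient's baseline value and y for the post-dose value. Protocol 10.8 asks for y − x in each patient. The minimum and maximum of x, and those of y, can come from different patients, so they do not recover y − x. Nor do they show whether an extreme value was already present before dosing.

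**Step 4, does adverse event reporting fill the gap?** Protocol 9.2.5.3 sends an abnormal result to the AE form when the investigator or the sponsor considers it clinically significant. Protocol 9.2.1.1 adds criteria: clinical signs or symptoms, need for intervention, a serious event, or an effect on study participation or treatment. SAP 6.7.1 lists and tabulates the events that are treatment-emergent. This captures selected abnormalities, not the values and changes of all patients.

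**Step 5, the named tests.** Even for its six items, SAP 6.9 does not mention the change from baseline in Protocol 10.8. It also gives no formula for creatinine clearance, which is not itself an item in the protocol panels.

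**The case against.** The strongest defence is that the selection is sensible. The protocol introduction describes a modest increase in bleeding as the main adverse effect in almost 5,000 adults and reports no specific off-target toxicity at the therapeutic dose. This is one dose, and development has stopped. Protocol 10.8 asks only for appropriate summary statistics and 10.3 leaves the details to the SAP. A subset built around bleeding and renal function is understandable on those terms. This argument stands against demanding tables for every analyte. It does not answer the per-patient change in Protocol 10.8, and the SAP does not offer it as a reason for the laboratory cut.

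A second defence is grammatical: the listing in SAP 6.9 could be read apart from the six named tests and so cover all laboratory data. That reading is strained. It would still leave platelets and liver tests without shift tables or out-of-range counts.

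A reader might also infer more than the documents support:

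- *That these results would appear nowhere in the report.* If SAP 6.1 applies, group summaries with minimum and maximum would appear, and an extreme value could show in them.
- *That a liver or platelet signal would surface only if an investigator chose to report it.* Protocol 9.2.5.3 also gives the sponsor that judgement, requires the investigator to monitor laboratory findings, and sits beside the explicit criteria in 9.2.1.1.
- *That renal function is equally missing.* Creatinine is partly covered through creatinine clearance.
- *That some 30 of 35 laboratory tests being unnamed is the right measure of the gap.* A raw count gives 17 CBC entries + 3 coagulation + 15 distinct chemistry tests = 35, of which 5 are named directly. But the 17 include a heading (differential) and overlapping neutrophil entries, and most of the rest have no bearing on liver or platelet safety.

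**Conclusion.** The point holds for platelets and the five liver tests. None of the six has a named listing, shift table or out-of-range count. Protocol 10.8 commits to change from baseline for each patient, and SAP 6.11 does not declare the departure. On planned numbers this concerns 42 post-dose panels.

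The conclusion rests on reading all three outputs in SAP 6.9 as tied to the six named tests. It also treats SAP 6.1 as a format rule that could at most supply group summaries. The 21 patients are the planned Part 1 total. The SAP says that the study was discontinued early, so the actual number of panels may be lower.

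The documents do not show that a safety signal was missed or that results were withheld. They show a gap in planned output that should be closed.

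**What to change.** In SAP 6.9, add platelets, ALT, AST, ALP, total bilirubin and GGT to the by-patient listing, the shift tables and the out-of-range counts. Add the change from baseline to 24 h and to 120 h that Protocol 10.8 promises, and state which pre-dose draw, screening or Day -1, is the baseline. In SAP 6.11, record any protocol laboratory test still left out, with the reason. If the listing was always meant to cover all tests, one sentence in 6.9 should say so.

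A count of patients who cross the laboratory limits in exclusion criterion 6 may seem a natural addition, but it is not workable as the protocol stands. That criterion gives two transaminase limits (≥ 2.5 × ULN and > 2 × ULN) and two bilirubin limits (≥ 1.5 × ULN, and > 2 × ULN with a direct-bilirubin condition), all under hepatic disease. Protocol 9.1.6.2 collects only total bilirubin. Those passages would have to be reconciled first.

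The cost is SAP wording and a few standard tables, with no new blood draws. It assumes that the values are in the database. The tests are run locally, per institution requirements. Protocol 11.4 requires data entry in general terms, but no section shows which analytes have eCRF fields. If some were not captured, SAP 6.11 should say so.

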#### 6.10. Vital Signs

A listing table will be provided for the vital signs.

## 6.11. Changes in the Conduct of the Study or Planned Analyses

The original study design included two parts: Part 1 and Part 2. Only Part 1 was conducted. The study was discontinued early because Portola decided not to continue developing the drug.

The original design called for measuring anti-fXa levels and thrombin generation in Part 1, however, this was not done.
